Effectiveness of Salbutamol Administration by Nebulizer versus Metered Dose Inhaler in Acute Asthma in Children in Suez Canal University Hospital Emergency

Department: A Randomized Control Trial

March 10th 2018

Study Protocol

Study design

Single-blinded randomized control trial.

Study location

Pediatric Emergency Department in Suez Canal University Hospital.

Study population

This study includes patients presenting with an acute exacerbation of asthma at the Pediatric Emergency Department in Suez Canal University Hospital.

Inclusion criteria:

- Children ranging from 2 – 14 years old.
- Both genders will be included.
- Patients with an acute exacerbation of asthma who were previously diagnosed with asthma.

Exclusion criteria:

- Patients with arrhythmia and cardiac diseases.
- Patients with thyroid diseases.
- Patients with bronchiolitis or pneumonia.
- Patients with status asthmaticus requiring immediate pediatric intensive care unit hospitalization.

Sampling

All children fulfilling the inclusion criteria will be included consecutively until the calculated sample size had been reached.

Sample size

The sample size was calculated using the following formula:

$$n = 2 \left[\frac{(Z_{\alpha/2} + Z_{\beta}) * \sigma}{\mu_1 - \mu_2} \right]^2$$

Where:

n = sample size

$Z_{\alpha/2} = 1.96$ (The critical value that divides the central 95% of the Z distribution from the 5% in the tail)

$Z_{\beta} = 0.84$ (The critical value that separates the lower 20% of the Z distribution from the upper 80%)

σ = the estimate of the standard deviation = 1.5

μ_1 = mean in the nebulizer group = 4.4

μ_2 = mean in the metered-dose inhaler group = 3.3

Therefore, by calculation, the sample size was equal to 30 cases per group, giving a total sample size of 60 cases.

Methods of data collection

Infants and children known to have asthma coming to the Pediatric Emergency Department of Suez Canal University Hospital and fulfilling the inclusion criteria will be assessed according to the following clinical respiratory score:

Assess	Score 0	Score 1	Score 2
Respiratory Rate	<2 months <50 2-12 months <40 1-5 years <30 >5 years <20	<2 months 50-60 2-12 months 40-50 1-5 years 30-40 >5 years 20-30	<2 months >60 2-12 months >50 1-5 years >40 >5 years >30

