Auscultation	Good air movement, expiratory scattered wheezing or loose rales/crackles	Depressed air movement, inspiratory and expiratory wheezes or rales/crackles	Diminished or absent breath sounds, severe wheezing, or rales/crackles or marked prolonged expiration
Use of Accessory Muscles	Mild to no use of accessory muscles, mild to no retractions OR nasal flaring on inspiration	Moderate intercostals retractions, mild to moderate use of accessory muscles, nasal flaring	Severe intercostals and substernal retractions, nasal flaring
Mental Status	Normal to mildly irritable	Irritable, agitated, restless	Lethargic
Room Air SpO2	> 95%	90-95%	<90%
Color	Normal	Pale to normal	Cyanotic, dusky

[figure not shown]
(Mild 0-3 moderate 4-7 severe 8-12)

The target population are patients who presented with moderate to severe wheezing (score 4-12).

Randomization will take place through a box that contained 60 thick envelopes, in which either nebulizer or spacer are written on 30 each, and each time an envelope is picked out by the assistant nurse in the emergency room to avoid any selection bias till our sample is fulfilled.

The assessment of the respiratory score before and after the treatment will be performed by an independent pediatrician resident who isn't involved in the decision-making and randomization of treatment. This physician will be asked to assess initially and then reassess after the equipment had been removed to avoid any bias.

CONSORT Flow Diagram to be filled in during the study:

Dosage and administration:

The nebulizer group will receive salbutamol aerosol solution (Farcolin® 0.121 gm/20ml solution) in a dose of 0.15 mg/kg weight, up to a maximum of 5 mg in 3.5 ml of normal saline solution. Aerosol is generated by jet nebulizers (Afnor oxygen flow meter) powered by oxygen and delivered via a face mask till the whole solution is vaporized every 20 min during the first hour (a maximum of three nebulization /hr). A flow rate of 7 L/min is used. (Liu, Covar, and Leung, 2016)

The metered dose inhaler with spacer group will receive two puffs of salbutamol (Ventolin® evohaler 100 mcg/puff) every 10 min 5 times over 1 hr with a maximum of 10 puffs/hr, using a spacer device with a face mask (Smart care chamber 500ml volume). Following each puff, the children will take 7 breaths from the spacer device held in place. (Rubilar, Castro-Rodriguez and Girardi, 2000)

Assessment:

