Patients will be reassessed after each treatment, if improved we can stop treatment and follow up after 2 hrs. Score <4 is considered a success while score>4 is failure of therapy. If not improved, we continue till the maximum number of treatment mentioned above.

Patients will be compared together according to the following characteristics: duration of treatment (preparation and delivery time), clinical outcome, patient satisfaction after treatment and hospitalization rate.

Each patient will have a form: Page 1 is an informed consent to be signed before randomization of treatment. Page 2 includes the following items that will be filled by parents after receiving the treatment;

1-personal data (name, age, address and telephone number). In addition, the researcher's phone number will be accessible to the patients.

2- Medical history (other illnesses, medications and degree of asthma either intermittent or persistent)

3-Clinical assessment (clinical respiratory score before and after treatment)

4-Patient satisfaction with given modality on a Likert scale from 1-5. This will be asked by the blinded assessor and included questions regarding:

- Comfort with modality used
- Duration of modality used
- Ease of administration
- Confidence in repeating treatment on their own at home if required

Statistical analysis of the data (Kotz et al, 2006)

Data will be fed to the computer and analyzed using IBM SPSS software package version 20.0. (Armonk, NY: IBM Corp) (Kirkpatrick, Feeney, 2013). Qualitative data will be described using number and percent. The Kolmogorov-Smirnov test is used to verify the normality of distribution. Quantitative data will be described using range (minimum and maximum), mean, standard deviation and median. Significance of the obtained results will be judged at the 5% level.

The used tests will be

1 - Chi-square test

For categorical variables, to compare between different groups (gender, address, satisfaction, admission)

2 - Fisher's Exact or Monte Carlo correction

Correction for chi-square when more than 20% of the cells have expected count less than 5

3 - Student t-test

For normally distributed quantitative variables, to compare between two studied groups (delivery and preparation time)

4 - Mann Whitney test

For abnormally distributed quantitative variables, to compare between two studied groups (age, percentage of improvement of clinical respiratory score and satisfaction).

Ethical Considerations

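### No primary outcome is named, the sample size is tied to no stated variable, and satisfaction is assigned to two tests with no rule for choosing between them

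*Combined protocol and SAP*

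**What the plan says.** **Outcomes.** The Assessment section says the groups will be compared on "duration of treatment (preparation and delivery time), clinical outcome, patient satisfaction after treatment and hospitalization rate". No section ranks these or calls any of them primary or secondary.

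**Significance.** Statistical analysis of the data gives one rule for everything: "Significance of the obtained results will be judged at the 5% level". No adjustment for several outcomes is mentioned.

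**Tests.** The chi-square entry reads "For categorical variables, to compare between different groups (gender, address, satisfaction, admission". The Mann-Whitney entry covers "age, percentage of improvement of clinical respiratory score and satisfaction". Satisfaction is in both. It is recorded on a 1-5 Likert scale covering four topics, and no combined score is defined.

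**The score.** Only percentage improvement is assigned a test. The Assessment section also states "Score <4 is considered a success while score>4 is failure of therapy", with no test attached.

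**Who assesses, and when.** Under Methods of data collection, an independent resident scores the child: "This physician will be asked to assess initially and then reassess after the equipment had been removed to avoid any bias". The Assessment section adds reassessment after each treatment and a follow-up at 2 hours.

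**Sample size.** The inputs are "mean in the nebulizer group = 4.4", 3.3 in the inhaler group and an SD of 1.5. No variable, unit or time point is given.

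**The concern.** The title asks about effectiveness, so a reader expects the respiratory score to decide the trial. The plan does not say so, and the sample-size section cannot fill the gap because its means belong to no named variable. Whoever analyses the data may therefore promote whichever outcome turns out significant, and nobody can say what difference 60 children give adequate power to detect.

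Satisfaction raises the same problem at the level of the test. Chi-square ignores the order of the five categories and Mann-Whitney uses it, so the same answers can be significant by one and not by the other.

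The success/failure rule adds a smaller difficulty. A score of exactly 4 falls in neither class, and the plan does not say whether this classification will be tested at all.

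**Working it through.** **1. The plan's own figure.** Inputs from the Sample size section: 1.96, 0.84, SD 1.5, difference 4.4 − 3.3 = 1.1.

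n = 2 × [(1.96 + 0.84) × 1.5 / 1.1]² = 29.16, rounded up to 30 per group.

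The arithmetic is right. A t-test at 30 per group with these inputs has power 79.8%. That figure belongs only to the unnamed variable.

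**2. Chance of at least one false positive.** Assumptions: each test has size 5%, and any single significant result is taken as a finding.

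| Setting | Result |
|---|---|
| Five true nulls (two times, score, satisfaction, admission), independent | 1 − 0.95⁵ = 22.6% |
| Same five, common correlation 0.3 / 0.5 / 0.8 (simulated normal statistics) | 20.9% / 18.3% / 12.7% |
| The two times truly differ, so three nulls remain, independent | 1 − 0.95³ = 14.3% |
| Same three, common correlation 0.3 / 0.5 / 0.8 | 13.6% / 12.6% / 9.8% |

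Admission may be rare. The plan switches to Fisher or Monte Carlo under this rule: "Correction for chi-square when more than 20% of the cells have expected count less than 5". At assumed admission rates of 5%, 10% and 15%, the exact size of chi-square with a switch to Fisher at 30 per arm is 0.15%, 1.2% and 2.9%. With the other tests independent, the five-null figure becomes 1 − 0.95⁴ × (1 − size) = 18.7%, 19.5% and 20.9%. The three-null figure, 1 − 0.95² × (1 − size), runs from 9.9% to 12.4%.

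**3. Does any rule in the plan choose the satisfaction test?** There are two selection rules. The normality check chooses between the t-test and Mann-Whitney. The expected-count rule chooses between chi-square and Fisher or Monte Carlo. Neither chooses between chi-square and Mann-Whitney.

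**4. Size of the satisfaction problem.** Simulations of one 1-5 item at 30 per arm, with assumed response distributions:

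- True odds ratio of 3 (assumed): power about 32-45% by chi-square and 43-67% by Mann-Whitney. The two verdicts differ in about 16-28% of trials.
- No true difference: each test alone is significant in about 3.5-5.4% of trials. If either may be used, the figure is 6.7-7.9%. This run used chi-square without the small-count correction.

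**5. Power for a score-based primary.** This applies only if 4.4 and 3.3 are after-treatment scores, which the plan does not say. Further assumptions: baseline mean 6-8, baseline SD 1.5-2.0, baseline-to-after correlation 0 to 0.7.

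- Mann-Whitney on the after-treatment score: power 76-77%.
- Mann-Whitney on percentage improvement: power 58-94%. Values below 70% arise only at zero correlation; at correlations of 0.3-0.7 the range is about 70-94%.

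**6. Splitting alpha instead.** Five co-equal outcomes under Bonferroni would each be tested at 0.05 / 5 = 1%. For the sized variable, t-test power at 30 per group falls from 79.8% to 57.3%. Naming one primary avoids this loss.

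**The case against.** **Success/failure may not be an endpoint.** The rule sits between the instructions on stopping and continuing treatment, outside the statistical section, and has no test. It can be read as a bedside label. A reader might infer that the trial has two rival clinical verdicts; in simulations under the assumptions of step 5, they disagree in 21-36% of trials. That figure applies only if success/failure is also tested for significance, which the plan does not state. The objection stands. What remains is that a score of 4 is unclassified and the role of the rule is unstated.

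**Satisfaction may be two variables.** Four questions are asked, so chi-square by question and Mann-Whitney on a combined score is a plausible reading. The plan does not say this and defines no combined score. The simulated figures describe a single item and should not be carried over to a total of four questions.

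**The familywise figure is an upper illustration.** 22.6% needs five true nulls, independence and any single win counting. Nothing in the plan says that one significant result decides the trial. This stands, and it is why the range matters more than the top value. It does not supply a ranking.

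**The sized variable is the implied primary.** This would answer the point if the variable could be identified, but the Sample size section does not allow that.

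**Conclusion.** The point holds on the text and does not depend on the simulations. Five comparisons are judged at an unadjusted 5% with none ranked, the variable behind 30 per group is unnamed, and satisfaction has two tests with no rule to choose. The plan can be followed to the letter while the deciding outcome or test is selected after results are seen.

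The size is illustrative: a familywise rate of 22.6% at most in the settings examined, 12.7-20.9% at correlations of 0.8 down to 0.3, and about 10-14% if the two times truly differ. For a single satisfaction item at an assumed odds ratio of 3, verdicts differ in about 16-28% of trials.

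A reader might go further and infer that the trial has a 22.6% false-positive rate, or that the sample size is wrong. The documents support neither. The first depends on how results are used, which is not stated. The second is contradicted by the arithmetic, which reproduces. The change should be made, but the point does not invalidate the design.

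**What to change.** Before outcome data by arm are seen:

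1. **Name one primary outcome** based on the clinical respiratory score assessed by the independent resident. The default is percentage improvement by Mann-Whitney at two-sided 5%, because that is the form for which the plan names a test. If 4.4, 3.3 and 1.5 are after-treatment scores, the sponsor may name that score instead. Fix which post-treatment assessment counts: for example, the last reassessment after the equipment is removed at the end of treatment, not the 2-hour follow-up. Fix the test in advance so that the Kolmogorov-Smirnov result cannot change it.
2. **State which variable 4.4, 3.3 and SD 1.5 describe.** If it is not the primary, restate the power for the primary at 30 per group and leave enrolment unchanged.
3. **Label the other outcomes secondary** and report them as supportive with 95% confidence intervals on a named effect measure, such as the Hodges-Lehmann difference for Mann-Whitney outcomes. If success/failure is reported, name chi-square or Fisher for it. The sponsor must also reconcile the wording so that a score of exactly 4 is classed.
4. **Remove satisfaction from the chi-square list.** Compare it by Mann-Whitney only, stating in advance whether by question or by a combined score.

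The cost is wording and a little analysis work. Secondary results carry less formal weight, and the stated power may become less favourable if the sized variable is not the primary.

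### Satisfaction is assigned to both chi-square and Mann-Whitney at the 5% level, with no rule for which result counts and no statement of whether its items are analysed separately or combined

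*Combined protocol and SAP*

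**What the plan says.** All the relevant text is in the combined protocol and SAP.

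- **Assessment, comparison list.** Treatment duration is compared between arms, together with "clinical outcome, patient satisfaction after treatment and hospitalization rate". Satisfaction is therefore one of four named comparisons.
- **Assessment, form item 4.** The instrument is given as "4-Patient satisfaction with given modality on a Likert scale from 1-5". The text continues "This will be asked by the blinded assessor and included questions regarding", followed by four topics: comfort, duration, ease of administration, and confidence in repeating the treatment at home.
- **Statistical analysis, test 1 (chi-square).** "For categorical variables, to compare between different groups (gender, address, satisfaction, admission" puts satisfaction among the categorical variables.
- **Statistical analysis, test 4 (Mann-Whitney).** "age, percentage of improvement of clinical respiratory score and satisfaction" puts it among the non-normal quantitative variables.
- **Rules for choosing a test.** Two are given: "Correction for chi-square when more than 20% of the cells have expected count less than 5" and "The Kolmogorov-Smirnov test is used to verify the normality of distribution".
- **Threshold.** "Significance of the obtained results will be judged at the 5% level". No multiplicity rule is stated.

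**The concern.** Satisfaction is the only variable named under two tests, once as categorical and once as quantitative. Neither rule for choosing a test resolves this. The expected-count rule only replaces chi-square by its exact or Monte Carlo version. The normality check bears on t-test versus Mann-Whitney, not on chi-square versus Mann-Whitney.

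The text allows at least four readings: Mann-Whitney decides; chi-square decides; both are run on the same score; or category counts go to chi-square and some score to Mann-Whitney. The last cannot be carried out as written, because no score is defined.

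The consequence depends on the reading. With two tests and freedom to cite either, the error rate exceeds 5%. With chi-square alone, error holds but the ordering of the 1-5 scale is discarded. With Mann-Whitney alone on a defined score, neither problem arises. The choice could be made after the data are seen, and the two tests can give opposite answers on the same data.

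**Working it through.** **1. Inputs.** Arm size is 30, from the Sample size section. The plan's figure reproduces: n = 2 × [(1.96 + 0.84) × 1.5 / (4.4 − 3.3)]² = 2 × (4.2 / 1.1)² = 29.16, rounded up to 30. That section does not tie the calculation to satisfaction. The scale is 1-5 and the threshold 5%. The documents give no satisfaction data, so every response distribution, effect size and inter-item correlation below is assumed.

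**2. Can the two tests conflict on the same data?** Take invented counts for ratings 1 to 5 of 1/3/8/10/8 in one arm and 3/6/10/7/4 in the other.

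- *Chi-square.* Expected counts per arm are 2, 4.5, 9, 8.5 and 6. The statistic is 2 × (1²/2 + 1.5²/4.5 + 1²/9 + 1.5²/8.5 + 2²/6) = 4.08 on 4 degrees of freedom. Four of ten cells (40%) have expected counts below 5, so the plan's sparse-cell rule applies. The Monte Carlo p-value is 0.42.
- *Mann-Whitney.* Mid-ranks are 2.5, 9, 22.5, 40 and 54.5. The first arm's rank sum is 2.5 + 27 + 180 + 400 + 436 = 1045.5, against 30 × 61 / 2 = 915 expected. The tie-corrected variance is (30 × 30 / 12) × [61 − 13206 / (60 × 59)] = 4295.2, so the SD is 65.54. With continuity correction z = 130 / 65.54 = 1.98 and p = 0.047.

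The conflict can also run the other way. Counts 8/2/4/4/12 against 2/8/10/8/2 give chi-square 18.25, p = 0.001, and Mann-Whitney z = 73.5 / 66.19 = 1.11, p = 0.27.

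**3. False positives if either test may count.** If the tests were independent, the rate would be 1 − 0.95² = 9.75%. They are correlated, so simulation is needed: one 1-5 score, 30 per arm, Pearson chi-square with a Monte Carlo p-value when more than 20% of expected counts are below 5, and two-sided tie-corrected Mann-Whitney. Across five assumed distributions (10,000 trials each) the either-test rate was 7.7-8.4%. Separately coded runs gave 7.9-8.5% and 7.9-8.7%. In the 10,000-trial runs chi-square alone gave 4.7-5.1% and Mann-Whitney alone 4.6-5.3%.

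**4. Power if chi-square alone decides.** Proportional-odds shifts, same assumed distributions:

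| Odds ratio | Chi-square power below Mann-Whitney (points) | Trials in which the tests disagree |
|---|---|---|
| 1.5 | about 4-6 | about 10-13% |
| 2 | 9-14 | 16-28% (odds ratios 2-4) |
| 3 | 16-23 | as above |
| 4 | 16-22 | as above |
| 6 | about 10-13 | about 10-12% |

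This kind of shift favours Mann-Whitney. If the arms differ only in spread, the order reverses:

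- 10/20/40/20/10% against 20% in each category: chi-square 31%, Mann-Whitney 5%.
- 5/15/60/15/5% against 25/15/20/15/25%: chi-square 91%, Mann-Whitney 7%.

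**5. Separate items or a combined score.** This assumes each of the four topics is scored 1-5. Unadjusted Mann-Whitney tests on four items give at least one false positive in 12-19% of trials as the assumed correlation falls from 0.8 to 0; the independence value is 1 − 0.95⁴ = 18.5%. Holm holds the familywise rate at 3.4-4.7%, and one test on a total gives 4.8-5.3%. Power at odds ratio 3:

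| Pattern | Total | Holm, at least one item |
|---|---|---|
| All four items shift the same way | 69-99% | 59-88% |
| Two items favour each arm | 5-11% | about 85-91% |

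Holm's power on a given item is 40-50%, against 56-65% unadjusted.

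**The case against.** The strongest objection is that the inflated error rate needs a decision rule the plan never states. The plan does not say that both tests will be run on the same score, or that either may count. It describes qualitative data by number and percent and quantitative data by mean, SD and median. That fits category counts going to chi-square and a score to Mann-Whitney. This stands: a reader might infer that the plan as written carries an 8-9% error rate, and the documents do not support that. Equally, nothing in them states the more benign reading.

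A second objection is that the instrument is not wholly undefined. The scale and four topics are given, and the natural reading is that each question is answered 1-5. This also stands. What is missing is narrower: whether and how items are combined, and which form goes to which test.

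Third, choosing Mann-Whitney is a preference, since chi-square alone also holds error near 5% and is much better for spread-only differences. That is a real cost, but an ordered rating is normally compared for a shift, and Mann-Whitney is already in the plan and uses that order.

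It could also be argued that the Mann-Whitney entry means percentage improvement in satisfaction. Satisfaction is collected only after treatment, so no improvement can be computed, and this reading would still leave satisfaction under that test.

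**Conclusion.** The point holds as an unresolved double assignment together with an unspecified analysis variable; the text alone establishes both. The 8-9% rate applies only if both tests are run on one score and either may count. The 4-23 point power loss applies only if chi-square alone decides and the arms differ by a proportional-odds shift of 1.5 to 6. Both figures rest on assumed distributions at 30 per arm and are illustrative.

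Two wider inferences should be resisted. The 12-19% figure for four unadjusted items is a separate multiplicity question and does not come from the double assignment. Nor does the ambiguity reach the other outcomes: satisfaction is not labelled primary and the sample size is not tied to it. The plan should be corrected, but the weight is moderate.

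**What to change.** Remove satisfaction from the chi-square list and add wording such as: *Each satisfaction variable is compared between arms by one two-sided Mann-Whitney test with tie correction. Category counts and percentages are shown without a test.*

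Then define the variable before analysis, choosing one of two forms:

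- **Separate item scores**, with the scoring of each item stated and a multiplicity method named; Holm is one option.
- **One combined score**, with its construction stated.

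The documents do not favour either. A total has more power when all items move together, but it can hide opposing item effects that Holm on the items would usually detect.

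The cost is wording only: the sample size stays at 30 per arm and data collection is unchanged, provided the chosen score uses the ratings the form already collects. The sponsor gives up a p-value for the category table and has little sensitivity to differences in spread alone (5-7% power in the two cases above).

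### Percentage improvement is read at a response-dependent stopping point, on different treatment grids in the two arms, so it can hide an inhaler advantage or suggest a nebulizer advantage that is not a device effect

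*Combined protocol and SAP*

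**What the plan says.** The Assessment section says: "Patients will be reassessed after each treatment, if improved we can stop treatment and follow up after 2 hrs". A child who has not improved continues to the arm's maximum. A score below 4 counts as success and above 4 as failure. Improvement itself is not defined, and stopping is permitted rather than required.

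Under Dosage and administration, the nebulizer arm is treated "every 20 min during the first hour (a maximum of three nebulization /hr") and the inhaler arm "every 10 min 5 times over 1 hr with a maximum of 10 puffs/hr". That gives up to 3 and up to 5 points at which treatment can stop.

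Under Methods of data collection, an independent resident scores each child at the start and again once the device is off. No clock time is attached to the second score. The patient form holds one score before and one after treatment. It has no item for a two-hour score or for the number of treatments given.

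The Statistical analysis section lists the Mann-Whitney test "For abnormally distributed quantitative variables, to compare between two studied groups (age, percentage of improvement of clinical respiratory score and satisfaction"). No other listed test uses the respiratory score. The chi-square variables are gender, address, satisfaction and admission; success at below 4 is not among them.

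**The concern.** If treatment ends when a child has improved and the score is taken then, responders in both arms finish just below the stopping level. A child who needed one treatment and a child who needed the full course can show the same percentage improvement. What separates them is how many treatments they needed, and the plan neither records nor tests that.

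The unequal grids add a second effect. If both full courses work equally well, each of 3 nebulizer steps is larger than each of 5 inhaler steps. Nebulizer children therefore tend to fall further below the stopping level before anyone looks.

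Two wrong conclusions become possible. A non-significant result may be reported as similar effectiveness when the nebulizer arm needed more treatment. A significant result for the nebulizer may be reported as a device effect when it comes from the spacing of the treatments.

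**Working it through.** **Step 1: the plan's own figure.** Inputs from Sample size: Z values 1.96 and 0.84, "the estimate of the standard deviation = 1.5", means 4.4 (nebulizer) and 3.3 (inhaler). n = 2 × [(1.96 + 0.84) × 1.5 / 1.1]² = 2 × (4.2 / 1.1)² = 29.16, rounded up to 30 per group. This agrees with the plan. Power at 30 per group is 81.1% by the normal formula and 79.8% for a t-test. The section does not say what outcome, unit or time point the means refer to.

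**Step 2: two single children.** Assumptions: the full-course drop is spread evenly over the sessions, scores are rounded, and treatment stops at the first score below 4.

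- *A real difference hidden.* Entry score 6; full-course drop 4.0 (nebulizer) or 5.1 (inhaler).
  - Nebulizer: 6 − 4/3 = 4.67, rounded 5; 6 − 8/3 = 3.33, rounded 3; stop. Improvement 3/6 = 50%.
  - Inhaler: 6 − 1.02 = 4.98, rounded 5; 3.96, rounded 4; 2.94, rounded 3; stop. Improvement 3/6 = 50%.
  - The full courses would have ended at 2 and 1 (67% and 83%).
- *A difference created.* Entry score 5; full-course drop 4.0 on either device.
  - Nebulizer: 3.67, rounded 4; 2.33, rounded 2; stop. Improvement 3/5 = 60%.
  - Inhaler: 4.2, rounded 4; 3.4, rounded 3; stop. Improvement 2/5 = 40%.
  - Both full courses would have ended at 1 (80%).

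**Step 3: simulation.** 30 per arm, two-sided Mann-Whitney test at 5% on (entry − final)/entry, 3 nebulizer against 5 inhaler sessions, stopping at a score below 4. Entry mixes, drops and the SD of the drop are assumptions. Drops are given as nebulizer/inhaler.

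| Setting, inhaler better by 1.1 | Power, no stopping | Power, stopping |
|---|---|---|
| Entry 4-9, SD 1.0, drops 4/5.1 | 68% | 10% |
| Entry 4-12, SD 1.5, drops 3/4.1 | 54% | 43% |
| Entry 6-12, SD 1.5, drops 2.5/3.6 | 67% | 65% |
| Entry 6-12, SD 1.5, drops 4/5.1 | 59% | 44% |
| Full-course final scores 4.4/3.3, SD 1.5, four entry mixes | 50-71% | 30-58% |

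The relative loss is (68 − 10)/68 = 85% in the first row and (54 − 43)/54 = 20% in the second. In the last row it is about 19-41%. The unstopped power there is already below 81% because percentage change brings in entry-score variation and the scores are rounded and bounded. That shortfall is a separate matter.

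*Nebulizer better.* With drops of 4.4/3.3 and entry 4-12, power rises from 51% to 72%. With full-course final scores of 3.3/4.4 it is 52-72% without stopping and 39-75% with it.

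*Equal full-course effects.*
- Entry 4-9 or 4-12: rejection about 4-14%. Other runs within 4-9 gave 15% when about 66% of children reached a score below 4, and 18-19% when about 78% did.
- Mild, high-response mixes: 23-28%, and 31% when about 91% reached a score below 4.
- Where rejection is inflated, nearly all of it favours the nebulizer.
- Identical assessment times in both arms: 4-5.5%. The false rejections therefore come from the unequal grids, not from stopping alone.

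*How far the size is open.* A further model with child-level variation in response gave 5-72% rejection for equal devices. If any fall in score counted as improvement, equal-device rejection ranged from 11% to 100% across models. If only half of the permitted stops are taken, the power loss shrinks but remains: 66-78% falls to 10-30% with entry 4-9 and SD 1.0, and to 37-64% with final scores 4.4/3.3.

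**The case against.** Five points can fairly be made against this.

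- *A reader might infer that the test loses most of its power as a rule.* The documents do not support that. Most of the power goes only when many children reach a score below 4, or under a loose reading of improvement. With severe entry scores the loss can be negligible (67% to 65%).
- *A reader might infer that the trial will miss the very difference it was sized for.* Sample size does not say whether 4.4 and 3.3 are final scores, which would favour the inhaler, or improvements, which would favour the nebulizer. In the second case power is not generally lost. The inference is unproven.
- *A reader might blame the Mann-Whitney test.* A t-test on the same scores would share the problem.
- *Other comparisons may cover the gap.* Duration of treatment is compared, and so is admission. If delivery time were totalled over sessions it would partly track treatments needed. The plan does not say that it is totalled, and it mixes device speed with response. This objection stands only in part.
- *Treat-until-improved may be the real question.* Then a different drop at stopping is a true difference between the two strategies as delivered. That is defensible, but the report would have to say so and could not attribute the difference to the device.

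It is also uncertain whether the analysed score is the one at stopping or one at the two-hour follow-up. The first is the natural reading, since the form holds a single after-treatment score and the resident scores when the device comes off.

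**Conclusion.** The concern holds in a conditional form. As written, the plan tests a score cut off at a point that depends on response, on a coarser grid in one arm than in the other.

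If the inhaler is the better device, power is lost: roughly a fifth to two fifths at final scores of 4.4 and 3.3, little with severe entry scores, and most of it when many children reach a score below 4. If the nebulizer is better, there is no general loss. With equal full-course effects, the unequal grids can push rejection above 5% in favour of the nebulizer. In the settings closest to the stated entry range this is modest (about 4-14%); with stopping at below 4 and evenly spread drops, it passed 20% only with mild entry and very high response.

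These sizes rest on assumed entry mixes, drops, even spacing of the response and stopping at below 4. None of these is fixed by the documents. The direction of the bias is better established than its size. The sample-size calculation reproduces and is not at fault.

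**What to change.** Leave the stopping of treatment as it is, and change what is recorded, compared and claimed.

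1. **Record.** Add to Page 2 of the patient form the number of treatments given (nebulizations or two-puff sessions), the time of the last one, and the time of the after-treatment score.
2. **Compare.** Keep the Mann-Whitney test on percentage improvement. Beside it, compare the number of treatments by common 20-minute block (nebulizations 1, 2, 3; inhaler sessions 1-2, 3-4, 5), and the proportion whose blinded final score is below 4. Tests already listed will serve: Mann-Whitney for the ordered blocks, chi-square or Fisher for the proportion.
3. **Sensitivity analysis.** Rank children with a final score below 4 by the block of their last treatment, and all others below them by final score. This should not replace the planned outcome. With entry 4-9 it had 44-67% power against 5-59% for percentage improvement when the inhaler is better. With entry 4-12 it had 25-28% against 22-60%, and only 11-22% against 73-90% when the nebulizer is better.
4. **Interpret.** State that percentage improvement is measured at the stopping point. Do not read a non-significant result as similar effectiveness, or a nebulizer advantage as a device effect, without the treatment counts.

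Scoring every child at one common time would remove the difference in reading times. It would not by itself restore the full-course comparison, because the documents do not show how a score moves after treatment stops.

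Cost: one count and two times on the form, two more comparisons and a few sentences of text; no extra patients or visits. The count partly reflects a stopping decision by staff who may know the device, so the below-4 status should come from the independent resident. Counts not recorded during the trial may be impossible to recover later.
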